**• Woman of Childbearing and Non-Childbearing Potential**

A woman is considered fertile following menarche and until becoming postmenopausal unless permanently sterile (see below).

If fertility is unclear (eg, amenorrhea in adolescents or athletes) and a menstrual cycle cannot be confirmed before the first dose of study intervention, additional evaluation should be considered.

Women in the following categories are not considered WOCBP:

**1. Pre-menopausal female with 1 of the following:**

- Documented hysterectomy
- Documented bilateral salpingectomy
- Documented bilateral oophorectomy

For individuals with permanent infertility due to a medical cause other than the above (eg, mullerian agenesis, androgen insensitivity), investigator discretion should be applied to determining study entry.

Note: Documentation for any of the above categories can come from the site personnel's review of the patient's medical records, medical examination or medical history interview. The method of documentation should be recorded in the patient's medical record for the study.

**2. Post-menopausal female:**

- A post-menopausal state is defined as no menses for 12 months without an alternative medical cause. In addition
- A high FSH level in the post-menopausal range must be used to confirm a post-menopausal state in women under 60 years of age and not using hormonal contraception or HRT
- A female on HRT and whose menopausal status is in doubt will be required to use one of the highly effective non-estrogen hormonal contraception methods if she wishes to continue her HRT during the study. Otherwise, she must discontinue HRT to allow confirmation of post-menopausal status before study enrollment

**• Contraception Methods**

Contraceptive use by men or women should be consistent with local availability/regulations regarding the use of contraceptive methods for those participating in clinical trials.

The following contraceptive methods are appropriate for this study:

**Highly Effective Methods That Have Low User Dependency**

1. Implantable progestogen-only hormone contraception associated with inhibition of ovulation
2. Intrauterine device
3. Intrauterine hormone-releasing system
4. Bilateral tubal occlusion
5. Vasectomized partner

- Vasectomized partner is a highly effective contraceptive method provided that the partner is the sole sexual partner of the WOCBP and the absence of sperm has been confirmed. If not, an additional highly effective method of contraception should be used. The spermatogenesis cycle is approximately 90 days.

### **Highly Effective Methods That Are User-Dependent**

6. Combined (estrogen- and progestogen-containing) hormonal contraception associated with inhibition of ovulation:
  - Oral + barrier\*
  - Intravaginal + barrier\*
  - Transdermal + barrier\*
7. Progestogen-only hormone contraception associated with inhibition of ovulation:
  - Oral + barrier\*
  - Injectable + barrier\*

### **Sexual Abstinence**

- Sexual abstinence is considered a highly effective method only if defined as refraining from heterosexual intercourse during the entire period of risk associated with the study intervention. The reliability of sexual abstinence needs to be evaluated in relation to the duration of the study and the preferred and usual lifestyle of the patient.

**APPENDIX E: LIVER SAFETY: SUGGESTED ACTION AND FOLLOW-UP ASSESSMENTS****Potential Cases of Drug Induced Liver Injury**

Humans exposed to a drug who show no sign of liver injury (as determined by elevations in transaminases) are termed “tolerators,” while those who show transient liver injury but adapt are termed “adaptors.” In some patients, transaminase elevations are a harbinger of a more serious potential outcome. These patients fail to adapt and therefore are “susceptible” to progressive and serious liver injury, commonly referred to as DILI. Patients who experience a transaminase elevation above  $3 \times$  ULN should be monitored more frequently to determine if they are “adaptors” or are “susceptible.”

In the majority of DILI cases, elevations in AST and/or ALT precede T bili elevations ( $>2 \times$  ULN) by several days or weeks. The increase in T bili typically occurs while AST/ALT is/are still elevated above  $3 \times$  ULN (i.e., AST/ALT and T bili values will be elevated within the same laboratory sample). In rare instances, by the time T bili elevations are detected, AST/ALT values might have decreased. This occurrence is still regarded as a potential DILI. Therefore, abnormal elevations in either AST OR ALT in addition to T bili that meet the criteria outlined below are considered potential DILI (assessed per Hy’s law criteria) cases and should always be considered important medical events, even before all other possible causes of liver injury have been excluded.

The threshold of laboratory abnormalities for a potential DILI case depends on the patient’s individual baseline values and underlying conditions. Patients who present with the following laboratory abnormalities should be evaluated further as potential DILI (Hy’s law) cases to definitively determine the etiology of the abnormal laboratory values:

- Patients with AST/ALT and T bili baseline values within the normal range who subsequently present with AST OR ALT values  $\geq 3 \times$  ULN AND a T bili value  $\geq 2 \times$  ULN with no evidence of hemolysis and an alkaline phosphatase value  $< 2 \times$  ULN or not available.

For patients with baseline AST OR ALT OR T bili values above the ULN, the following threshold values are used in the definition mentioned above, as needed, depending on which values are above the ULN at baseline:

- Pre-existing AST or ALT baseline values above the normal range: AST or ALT values  $\geq 2$  times the baseline values AND  $\geq 3 \times$  ULN; or  $\geq 8 \times$  ULN (whichever is smaller)
- Pre-existing values of T bili above the normal range: T bili level increased from baseline value by an amount of  $> 1 \times$  ULN or if the value reaches  $\geq 3 \times$  ULN (whichever is smaller)

Rises in AST/ALT and T bili separated by more than a few weeks should be assessed individually based on clinical judgment; any case where uncertainty remains as to whether it represents a potential Hy’s law case should be reviewed with the sponsor.

The patient should return to the investigator site and be evaluated as soon as possible, preferably within 48 hours from awareness of the abnormal results. This evaluation should include laboratory tests, detailed history and physical assessment.

In addition to repeating measurements of AST and ALT and T bili for suspected Hy's law cases, additional laboratory tests should include albumin, CK, direct and indirect bilirubin, GGT, PT/INR, total bile acids, and alkaline phosphatase. Consideration should also be given to drawing a separate tube of clotted blood and an anti-coagulated tube of blood for further testing, as needed, for further contemporaneous analyses at the time of the recognized initial abnormalities to determine etiology.

A detailed history, including relevant information, such as review of ethanol, acetaminophen/paracetamol (either by itself or as a co-formulated product in prescription or over-the-counter medications), recreational drug or supplement (herbal) use and consumption, family history, sexual history, travel history, history of contact with a jaundiced person, surgery, blood transfusion, history of liver or allergic disease, and potential occupational exposure to chemicals, should be collected. Further testing for acute hepatitis A, B, C, D and E infection, liver imaging (e.g., biliary tract) and collection of serum samples for acetaminophen/paracetamol drug and/or protein adduct levels may be warranted.

All cases demonstrated on repeat testing as meeting the laboratory criteria of AST/ALT and T bili elevation defined above should be considered potential DILI (Hy's law) cases if no other reason for the LFT abnormalities has yet been found. Such potential DILI (Hy's law) cases are to be reported as SAEs, irrespective of availability of all the results of the investigations performed to determine etiology of the LFT abnormalities.

A potential DILI (Hy's law) case becomes a confirmed case only after all results of reasonable investigations have been received and have excluded an alternative etiology.

## APPENDIX F: KIDNEY SAFETY: MONITORING GUIDELINES

### Laboratory Assessment of Change in Kidney Function and Detection of Kidney Injury

Standard kidney safety monitoring requires assessment of baseline and post-baseline (Scr measurement to eGFR [Scr-based eGFR]) or eCrCl.

Regardless of whether kidney function monitoring tests are required as a routine safety monitoring procedure in the study, if the investigator or sponsor deems it necessary to further assess kidney safety and quantify kidney function, then these test results should be managed and followed per standard of care.

### Age-Specific Kidney Function Calculation Recommendations

#### Adults (18 Years and Above)—2021 CKD-EPI Equations

2021 CKD-EPI Scr only	Scr (mg/dL)	Scys (mg/L)	Recommended eGFR Equation
Female	if $\leq$ 0.7	N/A	$eGFR = 143 \times (Scr/0.7)^{-0.241} \times (0.9938)^{Age}$
Female	if $>$ 0.7	N/A	$eGFR = 143 \times (Scr/0.7)^{-1.200} \times (0.9938)^{Age}$
Male	if $\leq$ 0.9	N/A	$eGFR = 142 \times (Scr/0.9)^{-0.302} \times (0.9938)^{Age}$
Male	if $>$ 0.9	N/A	$eGFR = 142 \times (Scr/0.9)^{-1.200} \times (0.9938)^{Age}$
2021 CKD-EPI Scr-Scys Combined	Scr (mg/dL)	Scys (mg/L)	Recommended eGFR Equation
Female	if $\leq$ 0.7	if $\leq$ 0.8	$eGFR = 130 \times (Scr/0.7)^{-0.219} \times (Scys/0.8)^{-0.323} \times (0.9961)^{Age}$
Female	if $\leq$ 0.7	if $>$ 0.8	$eGFR = 130 \times (Scr/0.7)^{-0.219} \times (Scys/0.8)^{-0.778} \times (0.9961)^{Age}$
Female	if $>$ 0.7	if $\leq$ 0.8	$eGFR = 130 \times (Scr/0.7)^{-0.544} \times (Scys/0.8)^{-0.323} \times (0.9961)^{Age}$
Female	if $>$ 0.7	if $>$ 0.8	$eGFR = 130 \times (Scr/0.7)^{-0.544} \times (Scys/0.8)^{-0.778} \times (0.9961)^{Age}$
Male	if $\leq$ 0.9	if $\leq$ 0.8	$eGFR = 135 \times (Scr/0.9)^{-0.144} \times (Scys/0.8)^{-0.323} \times (0.9961)^{Age}$
Male	if $\leq$ 0.9	if $>$ 0.8	$eGFR = 135 \times (Scr/0.9)^{-0.144} \times (Scys/0.8)^{-0.778} \times (0.9961)^{Age}$
Male	if $>$ 0.9	if $\leq$ 0.8	$eGFR = 135 \times (Scr/0.9)^{-0.544} \times (Scys/0.8)^{-0.323} \times (0.9961)^{Age}$
Male	if $>$ 0.9	if $>$ 0.8	$eGFR = 135 \times (Scr/0.9)^{-0.544} \times (Scys/0.8)^{-0.778} \times (0.9961)^{Age}$

Inker LA et al. N Engl J Med. 2021; 385:1737-49.

#### Adolescents (12 Years to <18 Years)—Cockcroft-Gault Formula

CrCl (mL/min)

Males: CrCl = [(140-age)  $\times$  body weight (in kg)] / [Scr (in mg/dL)  $\times$  72]

Females: CrCl =  $0.85 \times [(140-age) \times \text{body weight (in kg)}] / [\text{Scr (in mg/dL)} \times 72]$

**Children (2 years to <12 years)—Modified Schwartz Equation**

$\text{CrCl normalized to BSA (mL/min/1.73 m}^2\text{)} = (\text{K} \times \text{Ht}) / \text{Scr}$

Ht in cm; Scr in mg/dL.

K (proportionality constant): Female Child < 12 years: K = 0.55. Male Child < 12 years: K = 0.70

**Infants (1 month to <2 years) and Neonates (<1 month)—Bedside Schwartz Equation**

$\text{eGFR (mL/min/1.73 m}^2\text{)} = 0.413 \times (\text{Ht/Scr})$

Ht in cm ; Scr in mg/dL.

**Adverse Event Grading for Kidney Safety Laboratory Abnormalities**

AE grading for decline in kidney function (i.e., eGFR or eCrCl) will be according to CTCAE criteria.

**APPENDIX H: DOCUMENT HISTORY**

Version	Date
1.0	15 April 2021
2.0	17 June 2022

Summary of changes for Version 2.0, dated 17 June 2022 provided in a separate document.

## List of Abbreviations

Abbreviation	Definition
CCI	
CCI	
AE	Adverse Event
AESI	Adverse Event of Special Interest
ANC	Absolute Neutrophil Count
BMI	Body Mass Index
CDISC	Clinical Data Interchange Standards Consortium
CEC	Clinical Evaluation Committee
CI	Confidence Interval
CM	Concomitant Medications
CR	Complete Response
CRF	Case Report Form
CRO	Contract Research Organization
CSR	Clinical Study Report
CT	Computed Tomography
CTCAE	Common Terminology Criteria for Adverse Events
DCO	Data Cut-Off
DCR	Disease Control Rate
DES	DLT-Evaluable Set
DLT	Dose-Limiting Toxicity
DOR	Duration of Response
ECG	Electrocardiogram
ECHO	Echocardiogram
ECOG	Eastern Cooperative Oncology Group
eCRF	Electronic Case Report Form
EDC	Electronic Data Capture
EORTC	European Organisation for Research and Treatment of Cancer
EOS	End of Study
EOT	End of Treatment
FAS	Full Analysis Set
FDA	United States Food and Drug Administration
GCP	Good Clinical Practice
GLP	Good Laboratory Practice

Pfizer Inc. / Protocol: TTI-621-03/C4961003  
 IQVIA Biotech (Confidential) Project # YXA42460

h	hour
ICF	Informed Consent Form
ICH	International Council for Harmonisation
IgG1	immunoglobulin G1
IL	Interleukin
IP	Investigational Product
IR	Immune Response
IRB	Institutional Review Board

**CCI**

ITT	Intent-to-Treat
IU	International Units
IV	Intravenous
L	liter(s)
LVEF	Left Ventricular Ejection Fraction
m 	meter(s) squared
mAb	monoclonal antibody
MedDRA	Medical Dictionary for Regulatory Activities
mg/mL	Milligrams per milliliter
min	minute(s)
MTD	Maximum Tolerated Dose
MUGA	Multi-gated Acquisition Scan
NA	Not Available

**CCI**

NCI	National Cancer Institute
NE	Not Evaluable
ORR	Objective Response Rate
OS	Overall Survival
PD	Progressive Disease; Pharmacodynamics
PET	Positron Emission Tomography
PFS	Progression-Free Survival
PI	Principal Investigator
PK	Pharmacokinetics
PP	Per Protocol
PR	Partial Response
PRO	Patient-Reported Outcomes

Pfizer Inc. / Protocol: TTI-621-03/C4961003  
IQVIA Biotech (Confidential) Project # YXA42460

PT	Preferred Term
QA	Quality Assurance
QLQ-C30	Quality-of-Life Questionnaire Core 30
RECIST	Response Evaluation Criteria in Solid Tumors
SAE	Serious Adverse Event
SAP	Statistical Analysis Plan
SAS	Safety Analysis Set
SD	Stable Disease
SIRP $\alpha$	Signal Regulatory Protein $\alpha$
SOC	System Organ Class
SOP	Standard Operating Procedure
CCI	
TEAE	Treatment Emergent Adverse Events
TLF	Tables, Listings, and Figures
TNF $\alpha$	Tumor Necrosis Factor $\alpha$
TTP	Time to Progression
WHO	World Health Organization
WHO-DD	World Health Organization Drug Dictionary

Pfizer Inc. / Protocol: TTI-621-03/C4961003  
IQVIA Biotech (Confidential) Project # YXA42460

## 1. Introduction

### 1.1 Background

Soft tissue sarcomas are a rare, heterogeneous group of mesenchymal tumors, commonly the result of complex chromosomal abnormalities that play a role in disease progression and metastasis.

Doxorubicin has been since the 1970s the standard of care for first-line treatment of patients with metastatic or advanced soft tissue sarcoma; however, doxorubicin activity is poor, with a response rate of 9 - 27% (Schoenfeld, 1982; Judson, 2001) and progression-free survival of 3-5 months (D'Ambrosio, 2020; Penel, 2012; Italiano, 2012), with cumulative cardiac toxicity that limits its use (Borden, 1987).

Ontopacept, also known as TTI-621 or PF-07901800, is a recombinant soluble fusion protein designed to block the cell-surface protein CD47, which is found on the surface of many normal cell types and at high levels on many malignant tumor cells. CD47 binds to signal regulatory protein alpha (SIRP $\alpha$ ) on the surface of macrophages and inhibits their phagocytic activity. This CD47-mediated inhibition of macrophage phagocytosis activity is an important mechanism through which cancer cells can escape immune-mediated clearance, and high levels of CD47 correlate with poor clinical prognosis across a number of cancer types. PF-07901800 (TTI-621) combines **CCI** human SIRP $\alpha$  (the binding domain for CD47) with the Fc region of human IgG1, generating a decoy receptor for CD47 on the surface of tumor cells that both over-rides the CD47-mediated inhibition of phagocytosis through the SIRP $\alpha$  portion of the protein and provides a pro-phagocytic stimulation through the IgG1 moiety.

It is hypothesized that blockade of CD47-mediated immune evasion and concomitant activation of phagocytosis with PF-07901800 (TTI-621) will be clinically beneficial in patients with sarcoma subtypes in which CD47 is expressed and macrophage scores are increased. **CCI**

[REDACTED]

[REDACTED]

[REDACTED]

[REDACTED]

Thus, the primary goals of this clinical trial are to evaluate the safety of PF-07901800 (TTI-621) administered in combination with standard-of-care doxorubicin in anthracycline-naïve patients with high-grade soft tissue sarcomas and to further evaluate clinical activity and safety in the leiomyosarcoma subpopulation.

Pfizer Inc. / Protocol: TTI-621-03/C4961003  
IQVIA Biotech (Confidential) Project # YXA42460

## 1.2 Protocol and Amendment History

This Statistical Analysis Plan (SAP) is based on version 2.0 of Protocol TTI-621-03 (17JUN2022). This SAP will govern the analysis of data from this study. The plan for efficacy analyses may be modified prior to the clinical database lock. Any deviations from the analysis plan, will be documented as such in the clinical study report.

## 2. Study Objectives

### 2.1 Primary Objectives

[figure not shown]
- To evaluate the safety of escalating dose levels of PF-07901800 when administered in combination with 75 mg/m^2 doxorubicin in 21-day cycles and establish the maximum tolerated dose level of PF-07901800 when administered in combination with doxorubicin (Phase I Dose Escalation)
- To evaluate the safety of selected dose levels of PF-07901800 when administered in combination with 75 mg/m^2 doxorubicin in 21-day cycles and then as monotherapy in 28-day cycles until documentation of objective disease progression (Phase II Expansion)
- To investigate clinical activity assessed as overall response rate of PF-07901800 administered in combination with 75 mg/m^2 doxorubicin for up to six cycles (18 weeks) and then as monotherapy until documentation of objective disease progression (Phase II Expansion)

### 2.2 Secondary Objectives

- To further assess safety of the selected dose levels of PF-07901800 administered in combination with 75 mg/m^2 doxorubicin
- To describe other evidence of clinical benefit

[figure not shown]
2.3

CCI

Pfizer Inc. / Protocol: TTI-621-03/C4961003  
IQVIA Biotech (Confidential) Project # YXA42460

CCI

### 3. Study Endpoints

[figure not shown]
#### 3.1 Primary Endpoints

- Overall safety profile as assessed by the type, frequency, severity, timing and causal relationship of any adverse events, changes in vital signs, ECGs, serum chemistry or other laboratory assessment, treatment delays or discontinuations for patients enrolled into the dose escalation portion of the study
- Percentage of patients with objective response (CR + PR) as defined by RECIST v1.1 criteria

#### 3.2 Secondary Endpoints

- Overall safety profile as assessed by the type, frequency, severity, timing and causal relationship of any adverse events, changes in vital signs, ECGs, serum chemistry or other laboratory assessment, treatment delays or discontinuations for patients enrolled into the selected dose level cohorts in the expansion portion of the study
- Progression-free survival (PFS), overall survival (OS), disease control rate (DCR: CR + PR + SD), duration of response (DOR), duration of disease control, time to progression and time to new metastases as defined by RECIST v1.1 criteria, time to worsening of ECOG performance status, time to worsening of patient-reported outcomes assessments

CCI

3.3

Pfizer Inc. / Protocol: TTI-621-03/C4961003  
IQVIA Biotech (Confidential) Project # YXA42460  
CCI

[figure not shown]
Pfizer Inc. / Protocol: TTI-621-03/C4961003  
IQVIA Biotech (Confidential) Project # YXA42460

## 4. Study Design

### 4.1 Design Overview

Multi-center, open-label study designed to evaluate PF-07901800 administered in combination with doxorubicin. The first portion of the study will evaluate the safety of increasing dose levels of PF-07901800 in combination with doxorubicin at the standard dose of at 75 mg/m^2 in patients with high-grade soft tissue sarcoma. Two dose levels of PF-07901800 in combination with doxorubicin will be selected for further evaluation in an expansion phase in which patients with high-grade leiomyosarcoma.

The study will consist of a 28-day screening period, a treatment period in which patients will receive doxorubicin in combination with PF-07901800 in 21-day cycles for a maximum of six cycles, followed by continued treatment with PF-07901800 as monotherapy in 28-day cycles until documentation of objective disease progression or development of unacceptable toxicity, and a long-term follow-up period for assessment of overall survival.

### 4.2 Study Population

Eligible patients are those with high-grade soft tissue sarcoma who have not received more than one prior line of therapy (gemcitabine with docetaxel) and have not received an anthracycline in any setting (neoadjuvant, adjuvant or as treatment for advanced or metastatic disease). Up to approximately 80 patients are anticipated to participate in the study, with up to 18 in the dose escalation portion of the study and 31 in each of two expansion cohorts.

The protocol provides additional inclusion and exclusion criteria in its Section 6.

## 4.3 Sample Size Estimation

### 4.3.1 Dose Escalation cohorts

The number of patients will depend on the number of dose cohorts that will be enrolled before reaching the MTD. It is anticipated that three dose levels of PF-07901800 given in combination with a fixed dose of doxorubicin will be evaluated and that at least nine and up to approximately 18 patients will be enrolled to evaluate these three dose levels. On this basis of emerging safety data, additional dose levels may be added. The size and design of the dose escalation phase of the study is consistent with standard 3+3 design with the objective of determining the safety of escalating doses of PF-07901800 in combination with fixed dose doxorubicin and establishing PF-07901800 doses for further evaluation in the intended patient population.

### 4.3.2 Expansion cohorts

Expansion cohorts are initially planned to evaluate two PF-07901800 dose levels in combination with doxorubicin: a low dose of PF-07901800 (Cohort A) and a higher dose (Cohort B). A Simon two-stage design will be used for each dose cohort, assuming a baseline overall response rate of 10% with doxorubicin monotherapy in the Simon two-stage design and an alternative of 25%, a power of 90% and one-sided Type 1 error set at 0.20, each dose level cohort will require 18 patients enrolled and evaluable for response in Stage 1; with at least two clinical responses, an additional 13 patients will be enrolled in Stage 2. The combination will be considered worthy of further study if at least five clinical responses are observed in either 31-patient cohort.

To mitigate the risk of thrombocytopenia Grade 3 or Grade 4 observed at PF-07901800 highest dose 2mg/kg (Cohort B) on Day 8 during the combination therapy, PACL No 5 was issued to terminate enrollment into Cohort B after enrollment of the 18 patients (Stage 1) was completed. The remaining 13 patients, who were initially planned to be enrolled in Stage 2 Cohort B, were enrolled in an expansion Cohort C which was added to the study to evaluate a medium dose of PF-07901800 at 1 mg/kg. Simon's 2-stage design was not applicable for Cohort C.

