## 6. General Analytical Considerations

### 6.1 Study Summaries and Tabulations

The definition of “treatment group” will be tabulated as follows:

- Dose escalation cohorts (Phase 1)
  - Dose 1 (0.2 mg/kg)
  - Dose 2 (0.7 mg/kg)
  - Dose 3 (2.0 mg/kg)
- Expansion cohorts (Phase 2)
  - Cohort A (0.2 mg/kg)
  - Cohort B (1.0 mg/kg)
  - Cohort C (2.0 mg/kg)
- Pooled cohorts by dose level
  - Lower dose (0.2 mg/kg)

Pfizer Inc. / Protocol: TTI-621-03/C4961003  
IQVIA Biotech (Confidential) Project # YXA42460

- Higher dose (2.0 mg/kg)
- Overall
  - Phase 1 total
  - Phase 2 total
  - Phases 1 + 2 total (for non-efficacy summaries only)

Data will be summarized by treatment group as above, as applicable.

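### SAP 6.1 reverses the Cohort B and C doses given in SAP 4.3.2, the stated Simon power, alpha and rule can now describe only Cohort A, and the SAP defines no set for the Simon count

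*SAP*

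**What the plan says.** **Design and rule.** SAP 4.3.2 assumes a 10% response rate on doxorubicin alone and an alternative of 25%, with 90% power and one-sided alpha 0.20. It states that "each dose level cohort will require 18 patients enrolled and evaluable for response in Stage 1". Two or more responses open a second stage of 13, and the final rule is "The combination will be considered worthy of further study if at least five clinical responses are observed in either 31-patient cohort". Protocol 12.1.2 has the same design.

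**The change.** SAP 4.3.2 then says that "PACL No 5 was issued to terminate enrollment into Cohort B after enrollment of the 18 patients (Stage 1) was completed". The stated reason is Grade 3 or 4 thrombocytopenia "observed at PF-07901800 highest dose 2mg/kg (Cohort B) on Day 8". The remaining 13 patients went into an "expansion Cohort C which was added to the study to evaluate a medium dose of PF-07901800 at 1 mg/kg", and "Simon's 2-stage design was not applicable for Cohort C". Nothing is said about which power, alpha or rule applies to the cohort closed at 18. SAP 4.2 still anticipates 31 patients in each of two expansion cohorts.

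**Labels.** SAP 6.1 defines the treatment groups for the summaries. It lists "Cohort B (1.0 mg/kg" and "Cohort C (2.0 mg/kg", and also a pooled 2.0 mg/kg group.

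**Analysis sets.** Protocol 12.2 defines a response-evaluation population for the Simon design: expansion patients with at least two cycles and a post-treatment disease assessment, unless withdrawn earlier for safety or progression. SAP 6.7 defines only the FAS, the SAS (identical to the FAS) and the DES (dose escalation only). SAP 8 places all efficacy endpoints on the FAS and calls the analyses descriptive. SAP 8.2 reports response rates with Wilson intervals and all FAS patients in the denominator.

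**The concern.** The SAP was written after Cohort B had closed, yet it keeps text that assumes two 31-patient cohorts and disapplies the Simon design only for Cohort C. With the labels of SAP 6.1, that disapplication would fall on the 2.0 mg/kg group and leave the design attached to the 1.0 mg/kg group, the reverse of what SAP 4.3.2 describes. A programmer who works from SAP 6.1 by letter could mislabel columns or put the wrong expansion cohort into the pooled 2.0 mg/kg group.

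Two matters of interpretation are also left open. One is what may be concluded about the cohort closed at 18. The other is which patients count towards five of 31 in Cohort A, because the set that the protocol wrote for that count is absent from the SAP.

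**Working it through.** **1. Labels, side by side.**

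| | SAP 4.3.2 | SAP 6.1 |
|---|---|---|
| Cohort A | low dose (0.2 mg/kg anticipated in SAP 4.4) | 0.2 mg/kg |
| Cohort B | 2 mg/kg, closed at 18 | 1.0 mg/kg |
| Cohort C | 1 mg/kg, 13 patients, no Simon design | 2.0 mg/kg |

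Both cannot hold. Depending on which is followed, the expansion part of the pooled 2.0 mg/kg group has 18 patients (Cohort B) or 13 (Cohort C).

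**2. Reproduce the stated design.** Inputs from SAP 4.3.2: n1 = 18, n2 = 13, continue at 2 or more, succeed at 5 or more of 31, p = 0.10 or 0.25. With X1 ~ Bin(18, p) and X2 ~ Bin(13, p),

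P(success) = P(X1=2)·P(X2≥3) + P(X1=3)·P(X2≥2) + P(X1=4)·P(X2≥1) + P(X1≥5).

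At p = 0.10: 0.2835 × 0.1339 + 0.1680 × 0.3787 + 0.0700 × 0.7458 + 0.0282 = 0.0380 + 0.0636 + 0.0522 + 0.0282 = **0.182**.

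At p = 0.25: 0.0958 × 0.6674 + 0.1704 × 0.8733 + 0.2130 × 0.9762 + 0.4813 = 0.0639 + 0.1488 + 0.2079 + 0.4813 = **0.902**.

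The design meets its own limits (alpha at most 0.20, power at least 0.90), so there is no fault in the original calculation.

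**3. A cohort that ends at 18.** Binomial tails P(X ≥ r) for n = 18:

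| Cut-off r | p = 0.10 (alpha) | p = 0.25 (power) |
|---|---|---|
| 2 | 0.550 | 0.961 |
| 3 | 0.266 | 0.865 |
| 4 | 0.098 | 0.694 |
| 5 | 0.028 | 0.481 |

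Alpha of 0.20 or less needs r of 4 or more. Power of 0.90 or more needs r of 2 or less. No cut-off satisfies both, so the stated pair cannot describe this cohort under any rule. The row for r = 2 is the only count that the documents attach to 18 patients, and it is a continuation gate. At p = 0.10, P(X ≥ 2) = 1 − 0.9^18 − 18 × 0.1 × 0.9^17 = 1 − 0.150 − 0.300 = 0.550. A regimen no better than the assumed 10% passes it more often than not.

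**4. The set for the count.** SAP 4.3.2 asks for evaluable patients, and protocol 12.2 defines them. The FAS takes in everyone dosed at least once. The SAS is the same set, and the DES does not cover the expansion cohorts. The FAS would equal the protocol set only if no patient had been replaced. Protocol 5.1 and 12.3.3 require replacement of a patient whose leiomyosarcoma is not confirmed centrally, yet allow that patient to stay on treatment and so remain in the FAS. The gap begins partly in the protocol: 12.2 carries no histology condition, and 12.3.3 states exclusion from the response-evaluable population only for early withdrawals.

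**The case against.** The best reply is that the text largely answers the second item. The final rule is confined to 31-patient cohorts, a cohort of 18 plainly is not one, and SAP 4.3.2 describes two cohorts as initially planned and discloses the closure. The section is a sample-size rationale. No analysis section of the SAP applies a go/no-go test, SAP 8 makes efficacy descriptive, and the Wilson intervals proposed for the two smaller cohorts are already the SAP 8.2 output. SAP 4.2 speaks of anticipated numbers, and the total still fits: 18 + 31 + 18 + 13 = 80. All of this stands. It reduces the second item to a correction of stated properties.

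A reader might also infer that the missing set inflates the type I error, because a patient with unconfirmed histology could be counted as a responder alongside the replacement. The documents do not support that. They give no count of such patients, and the protocol says that the replacement is made to meet the study's statistical requirements. On a plain reading, the replaced patient does not also count towards them. What remains is an omission: the SAP should carry the protocol's set. Using the FAS as the default efficacy set agrees with the protocol.

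The reply does not reach the dose labels, which are a direct contradiction. The label error has no bearing on power or alpha and adds nothing to the Simon argument.

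**Conclusion.** Minor, on three counts.

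1. SAP 4.3.2 and 6.1 contradict each other on the doses of Cohorts B and C. This is the clearest error, because SAP 6.1 drives the tables and the pooled group. The passages must be reconciled; this review does not say which dose is right.
2. The stated 90% power and alpha 0.20 (exact 0.902 and 0.182) can describe only Cohort A, and only if it follows the 18 + 13 design in evaluable patients. No passage says that it passed Stage 1 or reached 31. Two or more responses among 18 must not be read as a positive result for the closed cohort. A reader might go further and say that the SAP claims a formal test or 90% power for that cohort as closed. It does not; it leaves the consequence of closure unstated.
3. The protocol's response-evaluation population has no counterpart in the SAP. No miscount is shown.

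The probabilities rest on the plan's own rates of 10% and 25% and on independent binomial responses.

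**What to change.** - **SAP 6.1:** reconcile the Cohort B and C doses with SAP 4.3.2, check the pooled 2.0 mg/kg group against the result, and identify cohorts by dose as well as letter throughout.
- **SAP 4.2 and 4.3.2:** state the cohort sizes as they now stand. Limit the 18/31 rule, with exact alpha 0.18 and power 0.90, to Cohort A, conditional on the 18 + 13 design. State that the cohorts of 18 and 13 receive a response rate with Wilson interval and no conclusion from the Simon rule.
- **SAP 6.7 and 8.2:** add the protocol 12.2 response-evaluation set for the Cohort A Simon count. State that patients replaced for unconfirmed histology are outside it, which is consistent with protocol 5.1 and 12.3.3 but not spelled out in 12.2. Keep the FAS response rate as the descriptive estimate.

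The cost is wording in five SAP sections and one extra responder count for Cohort A. Conduct does not change, and the planned descriptive tables stay apart from corrected cohort labels. SAP 1.2 allows the efficacy plan to be modified before database lock, and the change should be made by then.
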